We propose to enroll 600 AMSM and maintain a sample of 500 AMSM. We will use census information of population structure by race/ethnicity for each region to inform our recruitment goals. We will calculate the number of men in the eligible age group and by race/ethnicity in each region, and use data from the Youth Behavioral Risk Factor Surveillance System (YRBS) to estimate the proportion of AMSM in each age group who could meet eligibility criteria (based on same sex behavior, identity, or attraction), and apply that age-specific proportion to the estimated total AMSM population by race in each region. This will result in an estimated number of eligible AMSM per region and racial/ethnic group. Based on these calculations, to recruit a sample that is diverse in terms of race/ethnicity, we will need to oversample some racial/ethnic subgroups substantially. We will enroll a total of 150 AMSM from each of the 4 regions listed above. As noted, these regions were selected to represent variations in socioeconomic status, HIV prevalence, and rurality. Based on our estimates, we propose to sample such that at least 50% of our sample is a racial or ethnic minority, and at least 35% of participants being from rural areas across the regions. We recognize the challenge of recruiting early adolescents, especially because same sex attraction and same sex sexual experience become more common with age. Therefore, we realistically expect to include a greater number of participants in older age groups. These procedures will provide power for an analysis of efficacy stratified by age and race/ethnicity. Our expected sample size for analyses across both conditions is N=500 (Intervention, n=250; Control, n=250), assuming a 15-20% loss to follow-up. We estimated the minimum detectable effect sizes at 80% power, for comparisons of the two groups for the continuous primary cognitive (e.g., behavioral intentions, attitudes, norms, self-efficacy) outcomes, as well as the difference in the proportion of AMSM who report increased behavioral in the outcomes (e.g., condom use, HIV testing) to engage in HIV prevention services and behaviors in our treatment arm (iReach) vs. our attention-control arm. For mean differences, our sample size calculations are based on a two-sample t-test assuming equal variance using a two-sided significance of 0.05. At 80% power, we are able to detect a between-arm difference of $d=0.22$ at the final follow-up. For repeated measure analyses, assuming a within-person correlation of 0.25, we would be able to detect a difference of 0.08. A less favorable within-person correlation of 0.75 allows us to detect an effect size of 0.11. For proportions, our sample size calculations are based on a two-sample test of proportions using a two-sided significance of 0.05. To have 80% power to compare active treatment to the control group, we require at least 500 participants to find a 12.5% difference between treatment and control in cross-sectional analyses. Assuming within person correlation of 0.25, we can detect an 8.8% difference. A less favorable within-person correlation of 0.75 allows us to detect an 11.3% difference

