Eligible individuals must (1) have been assigned a male sex at birth and identify as male at the time of enrollment into the study (cis-gender male), (2) be between the ages of 13 and 18 years (inclusive), (3) speak and read English, (4) report same-sex attractions and/or behaviors, (5) have access to the Internet, (6) live in one of the zip codes at least partially contained in the 109 counties included in the four regions selected for this trial, and (7) self-report as HIV-negative at time of enrollment.

Randomization and Blinding

Participants are randomized on a 1:1 basis using a stratified randomization by race and region. AMSM will be randomized to one of two arms, with 300 randomized to each arm (complete data on 250 AMSM per arm, allowing for attrition of 50 AMSM per arm).

Study Assessments

The proposed domains mirror the theoretical framework informing our intervention. We include a summary of the primary and secondary outcomes, key intervention mechanisms of change, and potential covariates. Assessments will not take more than 25 minutes to complete. We have taken several steps to ensure that the assessments are brief and developmentally appropriate. First, AMSM will not answer all listed constructs at every assessment. Identity-related constructs, for example, will be measured at 6-month intervals, whereas other constructs (e.g., comfort discussing sexuality) will be assessed at each follow-up. Second, consistent with best practices that we have used in prior HIV studies with pediatric and adolescent populations^{142,256}, we will use gate-keeping questions to decide whether participants should receive other probes within a domain. For example, a participant who has yet to become sexually active would receive cognitive assessments focused on HIV risk and awareness (e.g., attitudes, norms), but would not receive questions regarding behavioral intentions to engage in HIV prevention in next 3 months (e.g., HIV testing, PrEP) or questions regarding sexual risk behaviors (e.g., sexual behavior, HIV testing, PrEP use). Similarly, at each assessment, AMSM with no lifetime substance use will not be asked about additional substance use questions. Among sexually active participants, gatekeeping also provides opportunities to regulate how detailed the assessments will be.

Domain	Assessment time					
	Baseline	Month 3	Month 6	Month 9	Month 12	Month 15
Primary outcomes						
HIV knowledge	X		X		X	X
Condom use/communication efficacy	X		X		X	X

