We will also collect information of the following mediators and moderators for our analyses: Socio-demographic information will include questions on race/ethnicity, educational attainment, employment status, place of birth, year of immigration (when appropriate), housing status, history of incarceration, and engagement in transactional sex. Psychological distress will be measured using existing, well-validated scales. We will use subscales from the Brief Symptom Inventory to measure depressive symptoms and anxiety symptoms. Depressive symptoms include 6 items ($\alpha > .80$) rated on a 5-point scale (1=never, 5 = very often). Items include feelings of loneliness, blue or sad, and having thoughts of ending one's life. Anxiety also includes 6 items ($\alpha > .90$) measured on the same 5-point scale and includes reporting nervousness or shakiness, feeling fearful, or suddenly scared for no reason. We will also measure AMSM's Perceived Loneliness using the UCLA Loneliness Scale using a 4-point scale (1=Never;4=Often). In our prior work, reliability for this scale with YMSM was high ($\alpha > .90$). To measure Stress, we will assess perceived stress through daily hassles. AMSM will rate their experiences of stress over the past month (e.g., how often have you found that you could not deal with all the things that you had to do), and rate the frequency with which they felt these ways on a scale from 1 (Never) to 5 (Very often). We have used these measures in prior studies and have shown excellent psychometric properties consistently over time. Social Media Use: Given potential disparities in access to technology, we will include the PEW Internet Survey questions regarding use of different devices, the number of hours spent online through each device, the reasons for social media use, sites commonly frequented, and extent to which the Internet supplements face-to-face interactions. We will also measure AMSM's frequency of use of social media to look for HIV or sexual health-related information, and their online partner-seeking behaviors. Online health seeking competency will be measured using an adapted, 6-item version of the eHealth Literacy Scale (eHEALS) that asks respondents on a 5-point Likert scale about their knowledge of online resources including where to locate them, how to find them, how to use information, and comfort with assessing the quality of online health information.

Missing Data

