Analysis tests the efficacy of the iREACH intervention as compared to a delayed intervention condition, to create positive changes in the following outcomes: *primary outcomes*: changes in confidence to engage in HIV prevention behaviors and changes in HIV knowledge and *secondary outcomes*: changes in sexual behavior and change in HIV testing behavior over the 12-month follow-up period. Descriptive statistics of the behavioral, psychosocial, and demographic characteristics of the participants will be described for all and by group (intervention and control). These will be compared between treatment groups using t-tests or Wilcoxon rank sum tests for continuous variables and chi-square tests for categorical variables. In addition, we will use the general framework of generalized linear mixed models (GLMM) to test for intervention effects over time. Note that some of our outcomes are binary, some count and some continuous traits and thus need to be treated differently. The general form of the GLMM will be $(\mu_{ij}) = \beta_{0i} + \beta_{\text{cov Covariates}_{ij}} + \beta_{\text{Time}_{j}} + \beta_{\text{Intervention Group}_i} + \beta_{\text{Group} \times \text{Time}_i}$, where μ_{ij} is the mean response corresponding to subject i at Time j (baseline and 4 follow-ups) with the appropriate link function (identity for continuous outcome, logit for binary outcome and natural log for count outcomes); Group =1 if the i -th subject is in the intervention group and 0 if the i -th subject is in the attention-control group. The interaction coefficients $\beta_{\text{Group} \times \text{Time}}$ are of interest here, measuring the difference in the rate of change in outcomes across the two treatment groups over time in the primary and secondary outcomes. Models will be compared according to information criterion like AIC, BIC. For some binary outcomes like HIV testing, we will perform an aggregate analysis after collapsing across the repeated measures using simple logistic regression comparing whether the probability of having tested at least once over the entire FU period is different across treatment groups, after adjusting for baseline values. To ensure robustness, we will also apply an exchangeable working correlation structure to its corresponding generalized estimating equation (GEE) model.

Reporting Conventions

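### Age at enrolment could be prespecified in the collapsed HIV-testing logistic model at almost no cost: a small gain in power for that analysis only

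*Protocol*

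**What the plan says.** **Age and experience.** In Target Population and Accrual, the Protocol explains the difficulty of recruiting early adolescents by noting that "same sex attraction and same sex sexual experience become more common with age". The justification under Key Inclusion Criteria adds that HIV-related risk behaviours start in adolescence and peak around the transition to adulthood. Eligibility is ages 13 to 18 in both documents.

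**Randomisation.** SAP, Randomization and Blinding: "Participants are randomized on a 1:1 basis using a stratified randomization by race and region". The Protocol's assignment section agrees, with national recruits forming a fifth region.

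**Covariates.** SAP, Covariates and Subgroups: "Socio-demographic information will include questions on race/ethnicity, educational attainment, employment status, place of birth", followed by other items. Age is not among them.

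**Efficacy models.** SAP, Efficacy Analyses, has two strands relevant here:
- A GLMM on baseline and four follow-ups, judged by the Group x Time coefficient, with a generic covariate term for which no variables are named and a GEE as robustness check.
- For some binary outcomes such as HIV testing, a logistic regression of any test during follow-up, "after adjusting for baseline values". This is the only named adjustment.

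**Where age does appear.** The Protocol's accrual section promises power for efficacy stratified by age. Its Statistical Analysis section puts age group into exploratory moderator regressions. The SAP carries over neither.

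**The concern.** Age is complete, measured before randomisation, and linked by the Protocol to sexual experience. Sexual experience in turn plausibly drives HIV testing. In a logistic model, leaving out a prognostic baseline variable costs some power for the treatment comparison. Because the SAP names no covariates beyond baseline values, the choice of whether to adjust for age is also left open until after the data are seen. What is at stake is a little power, and prespecification, in the collapsed HIV-testing analysis. The validity of the comparison is not in question.

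**Working it through.** **1. The plan's own figure for proportions.** The Protocol uses a "two-sample test of proportions using a two-sided significance of 0.05" and says "we require at least 500 participants to find a 12.5% difference between treatment and control in cross-sectional analyses". No control rate is given, so take rates centred on 50% (the worst case), 0.4375 and 0.5625:

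n per arm = [1.96 x sqrt(2 x 0.5 x 0.5) + 0.8416 x sqrt(0.4375 x 0.5625 + 0.5625 x 0.4375)]² / 0.125² = 250, or 500 in total.

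The figure reproduces. It allows for no covariate adjustment.

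**2. Gain in the collapsed HIV-testing model.**

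Input from the documents: 500 analysed, 250 per arm.

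Assumptions, none of them in the documents:
- 25% of controls test during follow-up.
- Treatment odds ratio 1.9. Applied directly to 25%, the odds are 0.333 x 1.9 = 0.633, or about 39%. That is a difference of the same order as the plan's 12.5 points.
- Log odds ratio 1.0 for having tested before baseline, already in the model.
- Ages weighted towards older youth.
- Age slopes of 0.2, 0.4 or 0.6 logits per year, acting on both baseline testing and the outcome.

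Method: 1,500 simulated trials per setting, fitted with and without age. Information gain is the squared ratio of mean z statistics.

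| Slope per year | Testing in previously untested controls, age 13 to 18 | Information ratio | Power without age | Power with age |
|---|---|---|---|---|
| 0.2 | 11% to 26% | 1.014 | 86.7% | 87.3% |
| 0.4 | 6% to 32% | 1.059 | 84.2% | 86.9% |
| 0.6 | 3% to 37% | 1.112 | 78.1% | 82.1% |

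Hand check: power with age = Φ[(1.96 + z_power) x sqrt(information ratio) - 1.96].
- 0.2: 3.072 x 1.0070 = 3.094, giving 87.2%.
- 0.4: 2.963 x 1.0291 = 3.049, giving 86.2%.
- 0.6: 2.736 x 1.0545 = 2.885, giving 82.2%.

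These agree with the simulation to within 1 point; the Monte Carlo standard error of one power estimate is about sqrt(0.8 x 0.2 / 1500) = 1 point. In participants, the gain is 500 x 0.014 = 7 up to 500 x 0.112 = 56.

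A repeat with different age weights gave 2%, 6% and 10% more information (power 89% to 90%, 85% to 87%, 80% to 84%). A separate simulation with other settings and lower starting power, at age odds ratios of 1.2, 1.4, 1.6 and 1.8 per year (0.18 to 0.59 logits), moved power from 77% to 78%, 70% to 72%, 69% to 74% and 66% to 72%. So 1 to 4 points is typical, and about 6 is the most seen.

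**3. The planned Group x Time test.** With a random intercept and baseline as a repeated outcome, a stable age effect cancels from the change contrast. The exact standard error of Group x Time, without and with an age main effect:

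| Within-person correlation | Complete data | 17% dropout, age R² 0.20 |
|---|---|---|
| 0.25 | 0.0980 and 0.0980 | 0.1037 and 0.1029 |
| 0.75 | 0.0566 and 0.0566 | 0.0606 and 0.0605 |

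With complete data the result is the same for age R² from 0.05 to 0.20. With dropout the reduction is at most 0.8%. For a binary GEE, simulated power was 60% with and without age at an odds ratio of 1.2 per year, and 56% with and without at 1.6. Age x Time can help only if trajectories differ by age. If age has the same correlation r with the outcome at baseline and follow-up (unit variances), its covariance with the change is r - r = 0.

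**The case against.** The opposing case is strong on scope, and most of it stands.

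- **The main efficacy test gains nothing.** Step 3 confirms this for an age main effect. What remains is one supplementary analysis of an outcome that the SAP text calls secondary, although the SAP assessment table lists HIV/STI testing under primary outcomes.
- **The age gradient is assumed.** The quoted sentence explains a recruitment difficulty. Neither document gives any association between age and testing, knowledge or self-efficacy, and the largest gain needs testing to rise from 3% to 37% over five years of age.
- **Gate-keeping cuts across the argument.** Both documents say that participants not yet sexually active skip the HIV-testing questions. If only those asked are analysed, the sample is below 500 and part of the path from age through sexual experience to testing is already conditioned on. If the others are counted as not tested, the gradient may be steeper.
- **Age is unspecified, not excluded.** The GLMM has an open covariate term. The covariate list describes survey content, and educational attainment, which is in it, probably tracks age at 13 to 18.

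Some stronger readings are tempting, but the documents do not support them:

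- *The continuous scales lose the equivalent of 1% to 13% of participants.* Those ratios (1.006 to 1.129) come from an ANCOVA of follow-up on baseline, for example (1 - 0.25²) / 0.8304 = 1.129 at within-person correlation 0.25 and age correlation 0.4. Neither document plans that model.
- *Behavioural outcomes suffer most.* No age-outcome association is given, and gate-keeping may flatten the gradient.
- *Omitting age undermines the missing-data approach.* The SAP's Missing Data section also plans nonresponse weights and multiple imputation, which can include age, and nothing in the documents shows that age predicts dropout.

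The objection does not remove the narrower point: the collapsed model names only baseline values, and age is free to add.

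**Conclusion.** The point holds in a limited form. Age is absent from randomisation, from the SAP covariate list and from the stated adjustment in the collapsed HIV-testing analysis. Including it there would yield about 1% to 11% more information and 1 to 4 power points, if testing rises with age by 0.2 to 0.6 logits per year and about 500 participants are analysed. With a weak gradient or a much smaller gated sample, the gain is close to nil.

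The gain is in power. In a logistic model, adding a prognostic covariate makes the treatment odds ratio conditional on that covariate; it does not shrink the standard error of the log odds ratio. Omitting age does not bias the randomised comparison. No benefit is shown for the Group x Time tests, and so none for the cognitive primary outcomes. Severity: minor, a free improvement.

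**What to change.** - In SAP, Efficacy Analyses, prespecify age in years at enrolment, beside the baseline value, in the collapsed HIV-testing logistic model and in any other collapsed binary outcome.
- Name age at enrolment in SAP, Covariates and Subgroups.
- Treat Age x Time in the GLMM as optional, to be included only if the team expects trajectories to differ by age.

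The cost is a few words in the SAP and one parameter per collapsed model. Age is already held for everyone through eligibility screening. The wording should be fixed before outcome data by arm are examined.

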HIV/STI testing	X		X		X	X
Outcomes required for analysis						
Demographics	X		X		X	X
Patient provider communication around sexual orientation		X		X		
Stigma		X		X		
Resilience		X		X		
Psychological needs	X		X		X	X
Future life goals		X		X		
Secondary outcomes						
Internalized homonegativity	X		X		X	X
PrEP use and willingness [X		X		X	X
Sex behaviors	X		X		X	X
Substance abuse	X		X		X	X
Depression	X		X		X	X
Anxiety	X		X		X	X
Self-Esteem	X		X		X	X
Covariates						
Peer influence		X		X		
Family support		X		X		
Discrimination		X		X		
Online behaviors		X		X		
Societal reaction to sexual orientation		X		X		
Ethnicity beliefs		X		X		
Relationship history	X		X		X	X
Intervention acceptability		X				

Sample Size

Our expected sample size for analyses across both conditions is N=600 (Intervention, n=300; Control, n=300), assuming a 15-20% loss to follow-up. We estimated the minimum detectable effect sizes at 80% power, for comparisons of the two groups for the continuous primary cognitive (e.g., behavioral intentions, attitudes, norms, self-efficacy) outcomes, as well as the difference in the proportion of AMSM who report increased behavioral in the outcomes (e.g., condom use, HIV testing) to engage in HIV prevention services and behaviors in our treatment arm vs. our attention-control arm. For mean differences, our sample size calculations are based on a two-sample t-test assuming equal variance using a two-sided significance of 0.05. At 80% power, we can detect a between-arm difference of $d=0.22$ at the final follow-up. For repeated measure analyses, assuming a within-person correlation of 0.25, we would be able to detect a difference of 0.08. A less favorable within-person correlation of 0.75 allows us to detect an effect size of 0.11. For proportions, our sample size calculations are based on a two-sample test of proportions using a two-sided significance of 0.05. To have 80% power to compare active treatment to the control group, we require at least 500 participants to find a 12.5% difference between treatment and control in cross-sectional analyses. Assuming within-person correlation of 0.25, we can detect an 8.8% difference. A less favorable within-person correlation of 0.75 allows us to detect an 11.3% difference.

Timing of Analyses

Final analysis will be conducted once the desired sample size is recruited has reached and completed the last study assessment.

Analysis Populations

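### The Protocol claims power for efficacy stratified by age and race/ethnicity, but no calculation supports this and, on the plan's own power basis, power within a stratum falls well short of 80%

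*Protocol*

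**What the plan says.** Protocol, Characteristics of the Study Population, section 1 (Target Population and Accrual), describes oversampling by race/ethnicity and then concludes: "These procedures will provide power for an analysis of efficacy stratified by age and race/ethnicity". Just before that it concedes that "we realistically expect to include a greater number of participants in older age groups". The only composition targets given are at least 50% racial or ethnic minority and at least 35% rural.

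The power text that follows concerns the whole sample. The basis is "We estimated the minimum detectable effect sizes at 80% power", and for means "our sample size calculations are based on a two-sample t-test assuming equal variance using a two-sided significance of 0.05". The results are "we are able to detect a between-arm difference of $d=0.22$ at the final follow-up" and, for proportions, "we require at least 500 participants to find a 12.5% difference between treatment and control in cross-sectional analyses". The analysed number is given as "Our expected sample size for analyses across both conditions is N=500 (Intervention, n=250; Control, n=250), assuming a 15-20% loss to follow-up". The SAP, Sample Size, repeats the effect sizes but with a different analysed number, "Our expected sample size for analyses across both conditions is N=600 (Intervention, n=300; Control, n=300), assuming a 15-20% loss to follow-up", and says nothing about subgroup power.

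Protocol, Study Procedures, section 5 (Statistical Analysis), calls the regressions on age group, race/ethnicity and rurality exploratory, plans tests of arm by subgroup interaction, and names three age groups (13-14, 15-16, 17-18). It gives the only subgroup sensitivity figure in either document: an interaction effect f of .18 at 80% power in a cross-sectional analysis.

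**The concern.** The sentence presents adequate subgroup power as a property of the design. A sample that is just large enough for an overall comparison cannot have similar power for the same effect in each of several parts of it. Oversampling evens out the strata but does not enlarge the total.

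Differential efficacy is a stated interest (Aim 4, and the Background section's expectation of larger gains in disadvantaged groups). A reader who relied on the accrual section could take a non-significant result in, say, the youngest group as evidence of no benefit there, when the study had little chance of showing one.

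**Working it through.** **Inputs from the documents.** Two-sided 0.05, 80% power, two-sample t-test, 250 per arm analysed, d = 0.22, within-person correlation 0.25 or 0.75, three age groups.

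**Assumed, because the documents do not say.** Stratum shares of the analysed sample (a half, a third, a quarter, a fifth, 15%), 1:1 allocation within each stratum, and the same effect in each stratum as overall.

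**1. The plan's own figures.**
- Detectable d = (1.960 + 0.842) × √(2/n per arm). With n = 250 this is 2.802 × 0.0894 = 0.251, not 0.22.
- Under the stated two-sided test, d = 0.22 has 69% power overall. It matches a one-sided 0.05 test (0.222). With 300 per arm the two-sided value is 0.229.
- The 12.5-point figure does reproduce at 250 per arm, for rates near 50%.
- Results are therefore given at d = 0.22 (as stated) and at d = 0.251 (which has 80% power at 250 per arm).

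**2. Power within a stratum, single final follow-up.** n per arm = 250 × share, noncentrality = d × √(n/2), two-sided t-test. For a third: n = 83.3, noncentrality = 0.22 × 6.455 = 1.42, power about 29%.

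| Share of 500 | n per arm | Power, d = 0.22 | Power, d = 0.251 | Detectable d at 80% |
|---|---|---|---|---|
| half | 125 | 41% | 51% | 0.35 |
| third | 83 | 29% | 36% | 0.43 |
| quarter | 62.5 | 23% | 28-29% | 0.50 |
| fifth | 50 | 19% | 24% | 0.56 |
| 15% | 37.5 | 15-16% | 19% | 0.65 |

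If age and race were crossed in an assumed 3 × 4 layout, a cell would hold about 42 participants and have about 11% power at d = 0.22. With all 600 analysed, as in the SAP text, a half, third and quarter have 48%, 34% and 27%.

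**3. Averaging follow-ups.** The variance of a mean of m follow-ups is multiplied by (1 + (m − 1)ρ)/m. At m = 4, ρ = 0.25 this is 0.4375, so the effective d is 0.22/0.661 = 0.333. Over m = 2 to 4 and ρ = 0.25 to 0.75, power at d = 0.22 is 46-75% for a half, 33-57% for a third and 26-45% for a quarter. The SAP assessment table schedules HIV knowledge and condom use/communication efficacy only at months 6 and 12 within the randomised comparison. For those outcomes m = 2 applies: 46-59%, 33-43% and 26-34%.

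**4. The stated repeated-measures effects of 0.08 and 0.11.** Using step 3 with m = 4, the detectable d in the full sample is 0.251 × 0.661 = 0.166 (ρ = 0.25) and 0.251 × 0.901 = 0.226 (ρ = 0.75). Half of each is 0.083 and 0.113. The stated values therefore look like Cohen's f (= d/2), which is an inference. They do not reproduce as d.

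**5. The interaction figure.** In a balanced 2 × 2 layout, f = .18 corresponds to a difference between subgroup effects of 4 × 0.18 = 0.72 SD, more than three times 0.22. A difference of 0.22 SD between two subgroup effects (f = 0.055) has about 23% power with 500.

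**The case against.** Several arguments run the other way.

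- *The subgroup plan is already cautious.* The Statistical Analysis section calls these analyses exploratory and plans interaction tests. Neither document prescribes a significance test in each stratum. A reader might infer that the trial will draw confirmatory conclusions stratum by stratum, but the documents do not support that. This stands, and it limits the consequence to one unquantified sentence that the SAP does not repeat.
- *Power of 20-30%.* A reader might infer this as a single headline figure. It needs equal thirds or quarters, one time point and d = 0.22. The documents do not define race strata, and they expect fewer young adolescents. A minority/white split gives 41%, so a range with its assumptions is the fair statement.
- *The repeated-measures effects.* Read as d, 0.08-0.11 would imply about 0.14-0.19 in a third (× √3) and 0.16-0.22 in a quarter (× 2), which would support the sentence. They do not reproduce as d (step 4).
- *The interaction f = .18.* It is not inflated: with 500, three groups allow f = 0.139 and four allow 0.148. But it concerns differences between subgroups, not efficacy within one.
- *Larger effects in some groups.* The Background section allows for this, but no such effect size is attached to the sentence.
- *Favourable combinations.* A reader might infer that no analysis could reach 80% in any stratum, which goes too far. With 600 analysed, four follow-ups and ρ = 0.25, a half reaches about 82%. Adjustment for baseline, which the plan's power text does not use, changes the factor in step 3 to (1 + (m − 1)ρ)/m − ρ². At ρ = 0.75, m = 4 this is 0.25, an effective d of 0.44, giving about 81% in a third and 69% in a quarter. At m = 2 it is 0.3125, giving about 87%, 71% and 59% for a half, third and quarter. The plan's figures treat higher correlation as less favourable, so they rest on no such gain, and the documents offer no calculation of this kind.

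**Conclusion.** The sentence is unsupported, and on the basis on which the plan states its power the design does not have the property claimed. At final follow-up with 500 analysed, within-stratum power for the stated d = 0.22 runs from about 41% (half the sample) to 15-16% (a 15% stratum). At the effect that has 80% power overall it runs from 51% to 19%. Averaging up to four follow-ups raises the ceiling to about 75% for a half, 57% for a third and 45% for a quarter.

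These results assume the stratum shares shown, 1:1 allocation within them, a common effect and no gain from baseline adjustment. The exact percentages would move with the real stratum sizes, which the documents do not give. The youngest age group is expected to be among the smaller ones. The point concerns a claim in the Protocol, not a defect in the planned subgroup models.

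**What to change.** In Target Population and Accrual, delete the sentence. Alternatively, replace it with the assumed stratum sizes and the detectable effect at 80% power for each: d about 0.35 for a half of 500, 0.43 for a third, 0.50 for a quarter and 0.56 for a fifth. Define the race/ethnicity groups. If the sponsor believes that repeated measures or baseline adjustment gives more, show that calculation with its correlation, number of follow-ups and effect scale.

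Align the passage with the Statistical Analysis section by saying that subgroup inference rests on the arm by subgroup interaction and that stratum estimates with intervals are exploratory. Most of that wording already exists there.

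The cost is a text change and a less favourable statement of subgroup power. The sample size, data collection and analysis model are unaffected.

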Intention-to-treat (ITT) All randomized study subjects. This will be seen as the primary population for the analysis. Per Protocol (PP) All randomized study subjects completing the whole study period (complete cases). For a specific analysis, study subjects with missing data on any of the variables in the model will be excluded from the analysis. Analyses of this population is seen as a sensitivity analysis to investigate whether conclusions are sensitive to assumptions regarding the pattern of missing data.

Covariates and Subgroups

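### The stated detectable difference of d=0.22 does not follow from its own inputs: the test described gives 0.251 at 250 per arm and 0.229 at 300, and the two documents attach the same d to different N

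*Protocol*

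**What the plan says.** The protocol (Characteristics of the Study Population, 1. Target Population and Accrual) sets the basis for continuous outcomes: "For mean differences, our sample size calculations are based on a two-sample t-test assuming equal variance using a two-sided significance of 0.05". It gives the sample as "Our expected sample size for analyses across both conditions is N=500 (Intervention, n=250; Control, n=250), assuming a 15-20% loss to follow-up", and then the result: "At 80% power, we are able to detect a between-arm difference of $d=0.22$ at the final follow-up".

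The SAP (Sample Size) repeats the test, the alpha, the power and the effect size: "At 80% power, we can detect a between-arm difference of $d=0.22$ at the final follow-up". Its analysis sample is different: "Our expected sample size for analyses across both conditions is N=600 (Intervention, n=300; Control, n=300), assuming a 15-20% loss to follow-up". Elsewhere the SAP (Randomization and Blinding) randomises 300 per arm and expects "complete data on 250 AMSM per arm, allowing for attrition of 50 AMSM per arm". Its primary population (Analysis Populations) is "All randomized study subjects. This will be seen as the primary population for the analysis".

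Both sample-size sections name behavioural intentions among the outcomes covered. Yet the SAP (Study Assessments) and the protocol (Methods, 2. Group Modifications) say that a participant who is not yet sexually active "would not receive questions regarding behavioral intentions to engage in HIV prevention in next 3 months".

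**The concern.** Everything needed to check the figure is stated: the test, alpha, sidedness, power and N. Because d is standardised, no SD is missing. The value given is more favourable than those inputs allow. It also stays the same when N moves from 500 in the protocol to 600 in the SAP, which cannot be right for one test at one alpha and power.

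This is the only detectable difference offered for continuous primary outcomes at the final follow-up. A reader who takes it at face value would put the chance of missing a true d of 0.22 at 20%. Under the stated test with 250 per arm it is 31%. That matters most if the trial ends with a null result that has to be interpreted.

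**Working it through.** **Inputs.** Two-sample t-test, equal variance, two-sided 0.05, 80% power (both documents). 1:1 allocation. Per arm: 250 (protocol; also SAP, Randomization and Blinding) or 300 (SAP, Sample Size). Loss of 15–20% from 600 leaves 600 × 0.85 = 510 to 600 × 0.80 = 480, or 255 to 240 per arm.

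**Trying to reproduce 0.22.** By the normal approximation, d = (z₀.₉₇₅ + z₀.₈₀) × √(2/n) = (1.960 + 0.842) × √(2/n).

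- n = 250: 2.802 × 0.0894 = 0.2506
- n = 300: 2.802 × 0.0816 = 0.2287

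The noncentral t gives nearly the same values:

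| Per arm with data | Detectable d at 80% power | Power at d=0.22 |
|---|---|---|
| 240 | 0.256 | 67% |
| 250 | 0.251 | 69% |
| 255 | 0.249 | 70% |
| 300 (no loss) | 0.229 | 77% |

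**N needed for 0.22.** n = 2 × (2.802/0.22)², which is 325 per arm by the normal approximation and 326 by the t distribution: 652 with data.

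**Rounding.** A true value as high as 0.2249 would print as 0.22, but power at 0.2249 is only 71% with 250 per arm and about 79% with 300.

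**One d, two N.** If 0.22 held at 250 per arm, the same test at 300 would give 0.22 × √(250/300) = 0.201.

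**Cross-check within the same paragraph.** Both documents say 500 participants are needed for a 12.5-point difference in proportions at the same alpha and power. Taking proportions centred on 50% (an assumption; no base rate is given), 43.75% against 56.25% needs 250 per arm, so that figure reproduces. Its standardised size is h = 2·arcsin√0.5625 − 2·arcsin√0.4375 = 0.251. At N=500 the proportions figure therefore agrees with a d of 0.25, and 0.22 is the outlier.

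**What could have produced 0.22.** These are possibilities only; neither document says so.

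- A one-sided 0.05 test at 250 per arm gives 0.223. The text says two-sided, and one-sided at 300 per arm gives 0.203.
- Baseline adjustment multiplies d by √(1 − r²). Reaching 0.22 needs r = √(1 − (0.22/0.2511)²) = 0.48 at 250 per arm, or √(1 − (0.22/0.2291)²) = 0.28 at 300.

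**Outcomes not asked of everyone.** The documents do not give the share of participants who will be asked the intention items, so the shares here are assumptions applied to 250 observed per arm:

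| Share asked | Per arm | Detectable d | Power at d=0.22 |
|---|---|---|---|
| 90% | 225 | 0.265 | 64% |
| 80% | 200 | 0.281 | 59% |
| 60% | 150 | 0.325 | 48% |
| 50% | 125 | 0.356 | 41% |

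Only the direction is documented. The main result does not depend on this table.

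**The case against.** The best defence is about weight. The trial was not sized to 0.22: the figure is reported as what a given N can detect. The efficacy test is the Group × Time term of a mixed model (protocol, Statistical Analysis; SAP, Efficacy Analyses), so 69% is not the power of the planned test. This is right, and it confines the point to the power statement. It does not make the statement correct, since the plan itself chose the t-test as its basis.

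The conflict over N can be read as loose labelling. Enrolling 600 and keeping about 500 is consistent elsewhere, and the SAP's primary population is everyone randomised, with likelihood methods that use partial data. That reading is fair and the fix adopts it. But 600 will not all be observed at the final follow-up under the stated loss, and even 600 observed does not give 0.22. At that N the gap is small (0.229, power 77%).

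Unstated baseline adjustment is also plausible. The paragraph mentions a within-person correlation of 0.25, and using it for adjustment at 300 per arm gives 0.2291 × √(1 − 0.25²) = 0.222. However, that correlation is attached to the repeated-measures figures, and the sentence at issue names a plain t-test.

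Lastly, the neighbouring repeated-measures values (0.08 and 0.11) are closer to the planned analysis. They are separate claims, not assessed here, and do not rescue an explicit statement about the final follow-up.

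**Conclusion.** The concern holds. With the test, alpha, power and N as written, the detectable difference is 0.251 at the protocol's 250 per arm and 0.229 at the SAP's 300 per arm with no loss. No input attached to the calculation gives 0.22, and rounding does not close the gap. The shortfall is 11 percentage points of power at 250 per arm (69% against 80%) and about 3 at 300 (77%). The SAP's use of 600 as the analysis sample after 15–20% loss conflicts with the protocol's 500 and with its own 250 per arm with complete data.

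The result rests only on stated inputs. Any further loss of power for intention items depends on an unknown share and is secondary. The design, enrolment and planned mixed-model analysis are not called into question. It should be corrected because readers will rely on the figure.

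**What to change.** In both documents, replace the d=0.22 sentence with wording such as:

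> With 600 randomised and 480 to 510 observed at the final follow-up (15–20% loss), a two-sample t-test at two-sided 0.05 has 80% power to detect d of about 0.25 (0.256 at 480, 0.249 at 510) for outcomes asked of all participants. For outcomes asked only of sexually active participants, such as behavioural intentions, the detectable difference is larger.

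Add the expected share asked, if it can be estimated. Alternatively, keep 0.22 and state and justify the assumption that yields it, for example a baseline-adjusted variance with its correlation.

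In the SAP's Sample Size section, label 600 as the number randomised (the intention-to-treat population) and about 500 as the number expected with data at the final follow-up.

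The cost is about two sentences per document and a slightly less favourable stated figure, with no added enrolment and no change to the analysis. While the paragraph is open, it would be sensible to check the adjacent repeated-measures figures and state their scale; that is additional work beyond this point.
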